### **9.3.2      Objectives and Outcomes**

The primary objective of this study is to investigate the correlation between changes from baseline to 52 weeks in FVC [% pred.] and changes from baseline to 52 weeks in dyspnea score [points] or cough score [points] as measured with the L-PF questionnaire over 52 weeks of nintedanib treatment in patients suffering from chronic fibrosing ILD with a progressive phenotype (excluding IPF):

- Correlation between change from baseline to week 52 in FVC [% pred.] and change from baseline to week 52 in dyspnea symptom score
- Correlation between change from baseline to week 52 in FVC [% pred.] and change from baseline to week 52 in cough symptom score

from each individual patient's difference between baseline and after 52 weeks of treatment with nintedanib. As such, comparisons will be made within treated population alone.

The questionnaire will be completed by the patient during each visit and will reflect the actual symptoms and the patient's status at that day, as described by the patient.

There will be no true comparison group of untreated patients in this study for a complete interpretation of findings since all patients in this study will receive nintedanib after their treating physician had decided for this therapeutic option for the respective individual patient.

Therefore, an untreated patient population will not exist. Further, the within-group comparison among treated patients before and after nintedanib initiation may not be ideal due to the process of progression itself during the follow up period which may limit the comparability of the two time-points.

#### 9.3.2.1 Primary outcomes

- Correlation between change from baseline to week 52 in FVC [% pred.] and change from baseline to week 52 in dyspnea symptom score
- Correlation between change from baseline to week 52 in FVC [% pred.] and change from baseline to week 52 in cough symptom score

[figure not shown]
The primary outcomes do not touch any safety question.

[figure not shown]
#### 9.3.2.2 Secondary outcomes

- Correlation between change from baseline to week 52 in FVC [mL] and change from baseline to week 52 in dyspnea symptom score; safety issue: no
- Correlation between change from baseline to week 52 in FVC [mL] and change from baseline to week 52 in cough symptom score; safety issue: no
- Absolute change from baseline in L-PF cough symptom score [points] at week 52; safety issue: no
- Absolute change from baseline in L-PF dyspnea symptom score [points] at week 52; safety issue: no

Primary and secondary outcomes will be analyzed for the Treated Set.

The secondary outcomes do not touch any safety question.

### **9.3.3 Covariates**

Covariates for adjustment will include patient demographics and disease characteristics. These will be discussed in the SAP.

## **9.4 DATA SOURCES**

Medical records collected through routine clinical care will be used to assess the inclusion/exclusion criteria of patients as well as for patient demographics, smoking history, collection of previous ILD medication, concomitant diseases, and concomitant medication, as well as for the health data of the patient during the course of the observation.

The LPF questionnaire will be provided as paper version to the patient to be filled out in writing at visits V1 to V5, as applicable.

All patients will be enrolled consecutively.

## 9.5 STUDY SIZE

In the INBUILD trial, patient groups on placebo vs nintedanib therapy differed in both their loss of FVC and dyspnea and cough symptom scores in the L-PF questionnaire (Figure 9.5:1; see below).

[figure not shown]

Figure 9.5:1 Changes from baseline to week 52 in L-PF symptoms dyspnea (left) and cough (right), domain scores respectively, seen in INBUILD

$\Delta$ FVC,  $\Delta$ dyspnea and  $\Delta$ cough symptom scores from INBUILD (see Table 9.5:1 below) were applied to estimate sample sizes.

Correlations between the change from baseline to week 52 in FVC (both FVC in mL and FVC as % predicted) and the change from baseline to week 52 in both L-PF dyspnea symptom score and cough symptom score measured by Pearson's correlation coefficient were  $\rho \approx -0.3$  in the Nintedanib arm of the treated set (see Table 9.5:1 below).

Table 9.5:1

Pearson correlation between the change from baseline to week 52 in FVC and the change from baseline to week 52 in L-PF symptoms scores in the Nintedanib arm (results were similar for the total population.)

Pearson correlation (change from baseline at week 52) between FVC and L-PF symptoms	Coefficient	95% Confidence interval	
		Lower	Upper
L-PF symptoms dyspnoe score and ...			
FVC in ml	-0.35	-0.45	-0.23
FVC (% predicted)	-0.37	-0.47	-0.26
L-PF symptoms cough score and ...			
FVC in ml	-0.26	-0.37	-0.14
FVC (% predicted)	-0.26	-0.37	-0.14

Currently, a meaningful threshold (“MCID”) has been published for neither the cough nor the dyspnea domain of the L-PF. However, should that information become available during the study, study results will be discussed in relation to meaningful thresholds (“MCID”) values.

Given a correlation  $\rho$  between change from baseline to week 52 in FVC [% pred.] and change from baseline to week 52 in dyspnea symptom score as well as change from baseline to week 52 in FVC [% pred.] and change from baseline to week 52 in cough symptom score of approximately -0.3, then 84 patient data sets would be required for evaluation. Assuming an estimated drop-out rate of approx. 15 % 100 patients will have to be recruited for this study. With this patient number (N = 84) and the assumption of a Pearson correlation of -0.3, the overall type I error is protected at the two-sided 0.05 level with a power of 80 %.

Therefore 100 patients are planned to be recruited for this NIS by about 20 specialists, experienced in treating ILD patients, (e. g., pulmonologists and rheumatologists) throughout Germany. Each investigator will include ca. 5 consecutive patients for whom the physician had decided for a treatment with nintedanib before actual recruitment of the patient. The treatment decision will have to have taken place before actual recruitment of the patient.

Due to the observational nature of the study, all analyses are exploratory. No weighting will be applied to either of the co-primary endpoints. All analyses in this observational study are exploratory. No weighting will be applied to either of the co-primary endpoints.

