Data sources:	In this NIS, information about the effect of a treatment with nintedanib on differences in cough and dyspnea scores, measured via the L-PF questionnaire, will be collected and this information will be assessed in relation to FVC from these patients' medical files in patients with chronic fibrosing ILD with a progressive phenotype from 100 patients in about 20 study centers throughout Germany by specialized physicians (pulmonologists, rheumatologists) experienced in the treatment of ILD patients.																				
Study size:	In the INBUILD trial, patient groups on placebo vs nintedanib therapy differed in both their loss of FVC and dyspnea and cough symptom scores in the L-PF questionnaire (Fig. 2; see below).																				
	
 <caption>INBUILD: Absolute change from baseline in L-PF symptoms dyspnea domain score at week 52 in overall population</caption>  
 Group	n	Adjusted mean (SE) absolute change from baseline in L-PF symptoms dyspnea domain score at week 52	
   
 Nintedanib	329	4.3	
 
 Placebo	323	7.8	
  
 
 <caption>INBUILD: Absolute change from baseline in L-PF symptoms cough domain score at week 52 in overall population</caption>  
 Group	n	Adjusted mean (SE) absolute change from baseline in L-PF symptoms cough domain score at week 52	
   
 Nintedanib	327	-1.8	
 
 Placebo	320	4.3	
  
			Group	n	Adjusted mean (SE) absolute change from baseline in L-PF symptoms dyspnea domain score at week 52	Nintedanib	329	4.3	Placebo	323	7.8	Group	n	Adjusted mean (SE) absolute change from baseline in L-PF symptoms cough domain score at week 52	Nintedanib	327	-1.8	Placebo	320	4.3
Group	n	Adjusted mean (SE) absolute change from baseline in L-PF symptoms dyspnea domain score at week 52																			
Nintedanib	329	4.3																			
Placebo	323	7.8																			
Group	n	Adjusted mean (SE) absolute change from baseline in L-PF symptoms cough domain score at week 52																			
Nintedanib	327	-1.8																			
Placebo	320	4.3																			

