## 10. DATA ANALYSIS

**Treated Set (TS):** All patients with signed informed consent who received at least one dose of nintedanib will be included in the treated set.

**Per Protocol Set (PPS):** All patients from the treated set who met all inclusion and exclusion criteria and did not violate any important protocol deviations.

Important protocol deviations:

- Dose interruption of nintedanib for more than 12 weeks and/or initiation of another antifibrotic therapy during the observation phase of the study.
- Missing patient questionnaires or other variables necessary for assessment of the primary study outcome
- Last patient visit completely missing (if no data is available for week 52)
- No FVC measurement available within 3 months prior to inclusion and FVC was not evaluated at baseline

All analyses will be performed on the treated set. Primary and secondary outcomes will be analysed for patients who have available data for the analysis of the efficacy endpoints. Additionally, all analyses for baseline and efficacy will be done on the per protocol set if  $\geq 10\%$  of the treated set is omitted.

All analyses on the treated and per protocol set will be performed using the method of time windowing: Only data will be used that was documented at performed visits within  $\pm 6$  weeks of the planned visit date (see 6.4 STUDY VISITS). For purpose of sensitivity primary and secondary endpoints will also be analysed without time windowing.

No subgroup analyses are planned due to the small number of patients.

For categorical variables summary tabulations of the number and percentage (%) relative to the treated set (unless otherwise specified, all patients in the patient set whether they have non-missing values or not) within each category of the parameter will be presented. The category missing will be displayed only if there are actually missing values.

For continuous variables number of values, mean, standard deviation, minimum, 25th percentile, median 75th percentile, maximum and number of missing values will be presented.

Percentages will be rounded to two decimal places.

No interim analysis is planned.

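### The 80% power in Protocol 9.5 holds only for 84 pairs at a correlation of -0.30; both inputs look optimistic against the plan's own INBUILD figures, most of all for cough

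*Protocol*

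**What the plan says.** Protocol 9.5 (repeated in the abstract) assumes a correlation of about -0.3 between the change in FVC % predicted and the change in each symptom score, and concludes: "then 84 patient data sets would be required for evaluation". It then allows for losses: "Assuming an estimated drop-out rate of approx. 15 % 100 patients will have to be recruited for this study". The power claim is conditional on that number: "With this patient number (N = 84) and the assumption of a Pearson correlation of -0.3, the overall type I error is protected". The power given there is 80%, for a two-sided test at 0.05. No source is given for the 15%.

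Table 9.5:1 gives the INBUILD nintedanib-arm correlations on which the -0.3 rests. For FVC % predicted they are -0.37 (95% CI -0.47 to -0.26) with dyspnea and -0.26 (-0.37 to -0.14) with cough. The abstract's INBUILD figure shows 329 nintedanib patients for dyspnea and 327 for cough. Protocol 9.2 and 9.3.1 state that the study's calculations and patient numbers are based on INBUILD.

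Several rules decide who contributes a pair. FVC is recorded if it is in the patient's data (Protocol 9.3). SAP 9.2 plans no general imputation. SAP 10 analyses the primary outcomes in patients with available data and applies visit windows: "Only data will be used that was documented at performed visits within" 6 weeks either side of the planned date. Protocol 9.3.1 and SAP 7.1 remove patients with an interruption of more than 12 weeks, or another antifibrotic, from the efficacy analysis.

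**The concern.** A correlation of changes needs four values per patient: FVC and the symptom score, each at baseline and at week 52. Drop-out is only one way to lose one of them. From 100 recruits the plan can lose 16 and still hold 84 pairs, so the margin is thin. The confidence intervals printed for INBUILD look too wide for 327-329 patients, which suggests that the source trial lost more pairs than 15%.

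Separately, one planning value of -0.30 covers two co-primary outcomes whose tabulated correlations are -0.37 and -0.26. It understates the first and overstates the second.

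At stake is how a weak result will be read. A cough correlation whose interval includes zero could be taken as evidence from a study with 80% power, when at the plan's own cough value the power is nearer two in three.

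**Working it through.** **1. The plan's figure.** With Fisher's z, n = ((1.960 + 0.842) / atanh(0.30))² + 3 = (2.802 / 0.3095)² + 3 = 84.9. Power at n = 84 is Φ(0.3095 × √81 − 1.960) = 79.6%; simulating the t-test of r gives about 80%. For recruitment, 84 / 0.85 = 98.8 and 85 / 0.85 = 100. The stated 84, 100 and 80% are reproduced.

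**2. Are the INBUILD intervals compatible with 327-329 pairs?** At those numbers Fisher-z intervals would be -0.46 to -0.27 for r = -0.37, -0.44 to -0.25 for r = -0.35, and -0.36 to -0.16 for r = -0.26. Table 9.5:1 prints wider limits in every row.

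**3. Implied number of pairs.** n = 3 + (2 × 1.96 / (atanh(upper) − atanh(lower)))². The rounding range covers every n that reproduces the printed two-decimal values.

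| Row of Table 9.5:1 | Width on z scale | Implied n | Rounding range | Share without a pair |
|---|---|---|---|---|
| Dyspnea, FVC % predicted | 0.2440 | 261 | 239-287 | 21% (13-27%) of 329 |
| Dyspnea, FVC mL | 0.2505 | 248 | 227-271 | 25% (18-31%) of 329 |
| Cough, both FVC rows | 0.2475 | 254 | 234-277 | 22% (15-28%) of 327 |

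If all rows share about the same n, the common range is 239-271. Then 271/327 = 82.9% and 239/329 = 72.6%, so about 17-27% had no pair. A 15% loss would mean 278 pairs (0.85 × 327) to 280 (0.85 × 329). Only the dyspnea / % predicted row allows that; the cough rows miss it narrowly (277).

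**4. Power.** Carried over to 100 recruits, the range is 73-83 pairs. Power is Φ(atanh(|ρ|) × √(n − 3) − 1.960), for each correlation separately; the simulated value is in brackets.

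| Pairs | ρ = -0.30 (planned) | ρ = -0.26 (cough, tabulated) | ρ = -0.37 (dyspnea, tabulated) |
|---|---|---|---|
| 84 | 79.6% (80%) | 66.8% (67%) | 93.8% (94%) |
| 83 | 79.1% (80%) | 66.3% (67%) | 93.5% (94%) |
| 77 | 75.9% (76%) | 62.9% (63%) | 91.6% (92%) |
| 73 | 73.5% (74%) | 60.5% (61%) | 90.1% (90%) |

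Reading down the first column, extra loss costs about 0-6 points. Reading across the first row, moving cough from -0.30 to -0.26 costs about 13 points with no extra loss at all.

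**5. Precision.** At r = -0.30 and 77 pairs, the 95% CI is tanh(−0.3095 ± 1.96/√74), or -0.49 to -0.08.

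**The case against.** The strongest reply is that the calculation is right: the 80% is expressly tied to 84 pairs and -0.30, and it reproduces. That stands. This is a question of planning assumptions, and a reader should not infer an arithmetic error.

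A reader might also infer that INBUILD lost 17-27% of its pairs and that 80% power is therefore out of reach. The documents do not support that. They report no pair count. The range assumes Fisher-z intervals, a similar n in every row, and the patient numbers in a figure of adjusted means as denominators. The two co-primary rows alone overlap up to 277 pairs, a loss of 15.3% of 327 or 15.8% of 329; only the secondary dyspnea / FVC mL row lifts the floor to 17%. At 83 pairs power is still about 80%. Applying INBUILD's losses to this study is a further assumption.

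The additional losses are not all one-way. Visit 6 schedules FVC and L-PF at week 52, if available, for patients who stopped early. The primary endpoints are also analysed without windowing as a sensitivity analysis. It is unsettled whether an interruption of more than 12 weeks removes a patient from the primary analysis: Protocol 9.3.1 and SAP 7.1 say the data leave the efficacy analysis, while SAP 10 lists it as a deviation affecting the per protocol set and runs all analyses on the treated set.

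Finally, all analyses are exploratory and every correlation is reported with a 95% CI, so precision will be visible. This limits the consequence. It does not make the power statement accurate for cough.

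**Conclusion.** The point holds as one about optimistic, partly unsupported inputs. The 15% has no source, sits at or beyond the favourable edge of what the printed INBUILD intervals allow, and is not said to include the other ways of losing a pair. Nothing in the analysis rules gives reason to expect smaller losses here than in a controlled trial. On the stated assumptions the effect at -0.30 is small: about 80% power at 83 pairs, 76% at 77 and 74% at 73.

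The firmer and larger finding does not depend on the back-calculation. At the cough correlation in the protocol's own table, power is about 67% with the full 84 pairs, and 61-67% with 73-83. Dyspnea at its tabulated value keeps at least 90% in every case. The 80% claim is thus unsupported by the plan's source table for one of the two co-primary outcomes. It should not be read as a failure for both, nor as a demonstration that the study is too small for its exploratory purpose.

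**What to change.** Keep 100 patients. In Protocol 9.5 and the abstract:

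- State that 80% power applies to 84 pairs at a correlation of -0.30.
- Add the planning range, labelled as inferred from the INBUILD interval widths and not as a reported rate: with 73-83 pairs, power is about 74-80% at -0.30, 61-67% for cough at -0.26, and at least 90% for dyspnea at -0.37. At r = -0.30 the 95% CI is about -0.49 to -0.08.
- Define the loss rate as patients without an analysable pair for any reason: missing FVC or L-PF, an out-of-window visit, or any efficacy exclusion.

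Reconcile Protocol 9.3.1 and SAP 7.1 with SAP 10 on whether patients with an interruption of more than 12 weeks leave the primary analysis or only the per protocol set.

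The cost is one paragraph, its copy in the abstract and one clarification of analysis sets, with a less favourable power statement for cough. No patient number, endpoint or method of analysis needs to change, apart from settling that rule.

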### **9.7.1 Main analysis**

For the analysis of the primary outcomes

- Correlation between change from baseline to week 52 in FVC [% pred.] and change from baseline to week 52 in dyspnea symptom score
- Correlation between change from baseline to week 52 in FVC [% pred.] and change from baseline to week 52 in cough symptom score

Pearson measures of correlation along with 95% two-sided confidence intervals and the two-sided p-values will be provided.

For the secondary outcomes

[figure not shown]
- Correlation between change from baseline to week 52 in FVC [mL] and change from baseline to week 52 in dyspnea symptom score
- Correlation between change from baseline to week 52 in FVC [mL] and change from baseline to week 52 in cough symptom score

Pearson measures of correlation along with 95% two-sided confidence intervals and the two-sided p-values will be provided.

The secondary outcomes

- absolute change from baseline in L-PF symptoms dyspnoea domain score between week 52 and baseline
- absolute change from baseline in L-PF symptoms cough domain score between week 52 and baseline

will be analyzed using a restricted maximum likelihood (REML) based repeated measures approach. Analyses will include the fixed, categorical effect of visit, as well as the continuous, fixed covariates of baseline and baseline-by-visit interaction. An unstructured (co)variance structure will be used to model the within-patient measurements.

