## 10.1 Main analysis

Due to the observational nature of the study, all analyses are exploratory. No weighting will be applied to either of the co-primary endpoints.

For the analysis of the primary outcomes

- Correlation between change from baseline to week 52 in FVC [% pred.] and change from baseline to week 52 in dyspnea symptom score
- Correlation between change from baseline to week 52 in FVC [% pred.] and change from baseline to week 52 in cough symptom score

Pearson measures of correlation along with 95% two-sided confidence intervals and the two-sided p-values will be provided.

For the secondary outcomes

[figure not shown]
- Correlation between change from baseline to week 52 in FVC [mL] and change from baseline to week 52 in dyspnea symptom score
- Correlation between change from baseline to week 52 in FVC [mL] and change from baseline to week 52 in cough symptom score

Pearson measures of correlation along with 95% two-sided confidence intervals and the two-sided p-values will be provided.

The secondary outcomes

- absolute change from baseline in L-PF symptoms dyspnoea domain score between week 52 and baseline
- absolute change from baseline in L-PF symptoms cough domain score between week 52 and baseline

will be analyzed using a restricted maximum likelihood (REML) based repeated measures approach. Analyses will include the fixed, categorical effect of visit, as well as the continuous, fixed covariates of baseline and baseline-by-visit interaction. An unstructured (co)variance structure will be used to model the within-patient measurements.

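### Protocol 9.5 claims 5% overall type I error with 80% power at N = 84; this is right for one correlation of -0.3 but not for two unadjusted co-primary tests, and cough power is about 67% at the protocol's own estimate

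*Protocol*

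**What the plan says.** Protocol 9.5 plans on a correlation of about -0.3 for both co-primary pairs and concludes "then 84 patient data sets would be required for evaluation". It then allows for attrition: "Assuming an estimated drop-out rate of approx. 15 % 100 patients will have to be recruited for this study". The error and power statement follows, tied to "the assumption of a Pearson correlation of -0.3": "the overall type I error is protected at the two-sided 0.05 level with a power of 80" per cent. The abstract carries the same sentence.

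Table 9.5:1 gives the INBUILD nintedanib-arm correlations with change in FVC % predicted: -0.37 for dyspnea (95% CI -0.47 to -0.26) and -0.26 for cough (95% CI -0.37 to -0.14).

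For the analysis, Protocol 9.7.1 says of the two primary correlations that "Pearson measures of correlation along with 95% two-sided confidence intervals and the two-sided p-values will be provided", and SAP 10.1 says the same. Neither mentions a multiplicity adjustment, a test order, or a criterion for overall success. Both documents say that the co-primary endpoints are not weighted, which is not an error-control rule. Protocol 9.5 also says "All analyses in this observational study are exploratory", and SAP 10.1 says "Due to the observational nature of the study, all analyses are exploratory".

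**The concern.** An *overall* type I error rate has meaning only when more than one test is counted. The sentence therefore reads as a 5% and 80% guarantee for the pair of co-primary results. The sample size, however, looks like the standard one for a single correlation at an unadjusted two-sided 0.05, and the analysis sections describe two such tests with nothing linking them.

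This is the only error and power statement given for the primary objective. If it is carried into the study report, two unadjusted p-values would be credited with familywise control that they lack. A non-significant cough result could also be read against a stated 80% power when, at the protocol's own cough estimate, it has about a one-in-three chance of occurring. A claim of protected overall error also conflicts with the declaration that everything is exploratory.

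**Working it through.** **Inputs.** From Protocol 9.5: two-sided 0.05, 80% power, planning correlation -0.3, N = 84, drop-out 15%, INBUILD estimates -0.37 (dyspnea) and -0.26 (cough). Not in the documents: the correlation between change in dyspnea and change in cough. It is assumed to lie between 0 and 0.7, with 0.9 as an extreme.

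**1. Reproducing 84.** For one correlation, Fisher's z gives

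n = ((z₀.₉₇₅ + z₀.₈₀) / atanh(0.30))² + 3 = (2.8016 / 0.3095)² + 3 = 84.9.

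Power at n = 84 is Φ(0.3095 × √81 − 1.960) = Φ(0.826) = 79.6%. With the small-sample bias term r/(2(n − 1)) it is 80.0%, and simulation of the t-test also gives 80.0%. Allowing for drop-out, 84 / 0.85 = 98.8, so 99, consistent with 100. At 0.025 per test the same formula gives 102.2, so 103. The protocol's 84 therefore belongs to one unadjusted two-sided 0.05 test.

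**2. Power per test at the table's estimates (n = 84, two-sided 0.05).**

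| Correlation | Power, Fisher z | With bias term | n for 80% | Expected 95% CI at n = 84 |
|---|---|---|---|---|
| -0.30 (planning) | 79.6% | 80.0% | 84.9 | -0.48 to -0.09 |
| -0.37 (dyspnea) | 93.8% | 94.0% | 55.0 | -0.54 to -0.17 |
| -0.26 (cough) | 66.8% | 67.3% | 113.8 | -0.45 to -0.05 |

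**3. The two tests together, unadjusted.** With independent test statistics, the error if either suffices is 1 − 0.95² = 9.75%. For correlated statistics it comes from the bivariate normal distribution. Power comes from simulated trivariate normal samples of 84 with a t-test on each correlation.

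| Assumed dyspnea-cough correlation | Error if either suffices | Power for both, -0.30/-0.30 | Power for both, -0.37/-0.26 |
|---|---|---|---|
| 0 | 9.75% | 63.7% | 63.2% |
| 0.3 | 9.51% | 66.4% | 64.4% |
| 0.5 | 9.07% | 68.5% | 65.6% |
| 0.7 | 8.35% | 71.0% | 66.6% |
| 0.9 | 7.04% | 74.8% | 67.3% |

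No row gives 5% error under the either rule, and no row gives 80% power under the both rule.

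**4. What Holm would give.** Holm holds overall error at or below 5%.

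| Assumed correlation | At least one, -0.30/-0.30 | Dyspnea at -0.37 | Cough at -0.26 | At least one, -0.37/-0.26 |
|---|---|---|---|---|
| 0 | 92.2% | 92.4% | 66.3% | 95.9% |
| 0.3 | 88.7% | 91.6% | 66.1% | 93.8% |
| 0.5 | 85.8% | 91.0% | 66.3% | 92.2% |
| 0.7 | 82.3% | 90.4% | 66.5% | 90.7% |
| 0.9 | 77.4% | 89.9% | 67.2% | 89.9% |

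At the planning value, Holm with success defined as at least one significant result would support the 5% and 80% claim for correlations up to 0.7, but not at 0.9. Neither document specifies Holm.

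**The case against.** The strongest defence is that *co-primary* often means both must succeed. The study hypothesis in the abstract names dyspnea and cough together, and the 80% is attached to a single correlation of -0.3. If both must succeed, two unadjusted 0.05 tests do keep overall error at or below 5%. If the 80% is per test, it is also right. But neither document states that rule, and the primary objective in Protocol 8 and SAP 5.1 joins the two scores with *or*. Under this reading the error rate would describe the pair and the power only one test, and the chance of meeting the rule would still be below 80%.

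A second defence is that -0.3 is an openly stated planning value. It lies inside both INBUILD intervals and close to the mean of the four table coefficients: (-0.35 - 0.37 - 0.26 - 0.26) / 4 = -0.31. This stands. The 84 is not wrong at its own assumption, and rounding is conservative for dyspnea as well as optimistic for cough. The 67% is itself a point estimate: across the INBUILD cough interval, power at 84 runs from about 24% (-0.14) to 94% (-0.37). What is missing is any statement of how uneven power is at the printed estimates.

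Third, all analyses are exploratory, the SAP does not repeat the type I error claim, and no decision hangs on either p-value. This limits the consequence but does not make the sentence correct. A study without multiplicity control should not claim a protected overall error rate.

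Finally, the joint and Holm figures rest on a correlation that the documents do not supply. They are illustrations with a stated range and should be used only as such.

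**Conclusion.** The concern holds. N = 84 gives two-sided 5% error and 80% power for one correlation of -0.3. The described analysis does not give both for the pair: about 8.4% to 9.75% error if either result suffices, or about 64% to 71% power if both are required at -0.3 (63% to 67% at the INBUILD estimates). These joint ranges assume a dyspnea-cough change correlation of 0 to 0.7. The shortfall narrows as that correlation rises but is still present at 0.9.

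The per-test figures of about 94% for dyspnea and 67% for cough do not depend on that assumption, only on the INBUILD point estimates. Since the analyses are exploratory and confidence intervals are reported, this is a stated operating characteristic that should be corrected, not a failure of the design.

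**What to change.** In the abstract and Protocol 9.5, delete *overall* and replace the sentence with wording such as:

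> N = 84 gives 80% power for each correlation tested separately at two-sided 0.05, unadjusted for two co-primary tests, if rho = -0.3. At the INBUILD estimates, power is about 94% (dyspnea) and 67% (cough).

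That is enough for analyses declared exploratory. Any joint power or familywise error that is quoted should be a range with its assumed dyspnea-cough correlation.

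If the sponsor prefers to keep the overall error claim, add one sentence to SAP 10.1 applying Holm to the two co-primary p-values. Then quote the Holm power with its assumption: about 90% to 92% for dyspnea, 66% to 67% for cough and 91% to 96% for at least one, at the INBUILD estimates and a correlation of 0 to 0.7. If the 80% at -0.3 is to rest on at least one success, note that it drops to about 77% at a correlation of 0.9.

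The first option costs only wording, and the stated power for cough becomes less favourable. Holm costs about 2 to 4 points of power for dyspnea and 1 for cough. Neither option adds patients, and neither brings cough to 80%, which would need about 114 evaluable patients.
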